Clinical Investigation Protocol (incl. statistical considerations)

Clinical examination of the F-Composite 2 Systems in the direct filling therapy

(NCT03221660)

INDEX

1. OBJECTIVES AND HYPOTHESES OF THE CLINICAL INVESTIGATION	3
2. GENERAL OVERVIEW OF THE CLINICAL INVESTIGATION	4
3. JUSTIFICATION FOR THE STRUCTURE OF THE CLINICAL INVESTIGATION.....	4
4. INVESTIGATORS	5
5. MATERIALS	5
6. RISKS AND BENEFITS OF THE INVESTIGATIONAL PRODUCT AND THE CLINICAL INVESTIGATION	6
7. STRUCTURE OF THE CLINICAL INVESTIGATION.....	7
7.1 GENERAL INFORMATION	7
7.2 PRODUCTS AND REFERENCE PRODUCTS	8
7.3 PARTICIPANTS (IN-/EXCLUSION CRITERIA).....	9
7.4 TREATMENTS	10
7.5 SPECIFICATIONS FOR MONITORING	11
8. STATISTICAL CONSIDERATIONS	12
9. DATA MANAGEMENT.....	12
10. CHANGES TO THE CLINICAL INVESTIGATION PROTOCOL	13
11. DEVIATIONS FROM THE CLINICAL INVESTIGATION PROTOCOL.....	13
12. PROOF OF USE OF THE PRODUCT.....	13
13. DECLARATION OF CONFORMITY	13
14. PROCEDURE FOR OBTAINING CONSENT	14
15. ADVERSE EVENTS, ADVERSE EFFECTS OF THE PRODUCT AND PRODUCT DEFECTS..	14
16. POPULATION THAT CAN BE PRESSURED	14
17. PREMATURE TERMINATION OR SUSPENSION OF THE EXAMINATION	15
18. PUBLICATION POLICY	15
19. REFERENCES	15

1. Objectives and hypotheses of the clinical investigation

a) The aim of this prospective study is to evaluate the clinical performance of F-Composite 2, a proven flowable bulk material and adhesive system for the restoration of masticatory posterior fillings (Class I and II), all three materials being polymerized with Bluephase PowerCure (flash mode).

b) Primary hypotheses to be accepted or rejected by statistical data from the clinical investigation.

[name]. [name] from the Biostatistical Department of the Institute of Social and Preventive Medicine at the University of Lausanne, Switzerland, has performed a case number calculation. Assuming that a maximum of 10% post-operative hypersensitivity is acceptable, but actually only 5% is expected, the following formula can be used to calculate the case number (80% power, using a chi-square test at 5% probability of error)

$$N = (1.96 * \sqrt{0.95 * 0.05} + 0.84 * \sqrt{1 * 0})^2 / (1 - 0.95)^2 = 73 \text{ participants or fillings}$$

Furthermore, if one assumes - based on internal experience - that after one year there is a drop-out rate of 2%, 75 fillings are necessary at the beginning of the study to statistically confirm the primary endpoint (post-operative hypersensitivities).

(c) claimed and intended performance of the test product, which shall be demonstrated.

The following working hypotheses should be clarified:

- Teeth restored with the F-Composite 2 system have postoperative hypersensitivity in a maximum of 10% of cases after 1 month.
- A maximum of one tooth shows a loss of vitality within 12 months.
- With the selected application protocol, the F-Composite 2 system enables a filling quality at least comparable to F-Composite (see study "Clinical investigation of Flash Composite in direct restorative therapy" CEC-ZH No. 2011-0150/5.) After 2 years a maximum of 3 fillings should be replaced due to poor quality.

(d) The following risks shall be assessed:

- post-op discomfort. In almost all clinical studies with direct filling materials, postoperative hypersensitivity occurs in the range of a few percent of the treated teeth. Whether the probability of occurrence is increased when using the F-Composite 2 restorative system can only be estimated by a clinical study.

- Inflammation/death of the pulp (the "dental nerve"). In December 2015 a clinical study was completed after an observation period of three years (KEK-ZH No. 2011-0150/5), in which the filling material was polymerized with 10 000 mW/cm² for one second, but without exposing the adhesive to this light intensity. No permanent damage to the pulp due to the high light intensity or temperature gradient was observed. In addition, Bluephase PowerCure was used to investigate the temperature gradient in the pulp in in vitro studies on extracted teeth. The absolute temperature was comparable to other lamps (recorded in investigator's brochure). However, the temperature gradient was steeper.

- Cracks in the tooth structure or between tooth and restoration or marginal gaps which could lead to discoloration, secondary caries, filling fracture, filling loss or tooth fracture. In very severely hollowed cavities on extracted molar teeth with undercuts (worst-case scenario) under the cusps, horizontal cracks in the tooth structure could be observed in vitro in bulk fillings with the flowable composite (recorded in validation report examiner brochure). For this reason, special attention is also paid to this point during the clinical investigation.

- Unexpected changes in the filling surface that could lead to roughness, discolouration or increased wear of the material. As the material is similarly polishable as a conventional composite material, it is expected that no more surface discolouration will be observed.

2. General overview of the clinical investigation

The F-Composite 2 system is a coordinated system of filling materials, adhesive and polymerization unit for direct restorative therapy in dentistry.

The aim of this single-arm prospective clinical study is to investigate the F-Composite 2 system in direct filling therapy of class I and II cavities.

The following working hypotheses should be clarified:

- Teeth restored with the F-Composite 2 system have postoperative hypersensitivity in a maximum of 10% of cases after 1 month, which corresponds to a frequency as described in the literature.
- With the selected application protocol, the F-Composite 2 system enables at least comparable restorative quality to F-Composite (see study "Clinical investigation of Flash Composite in direct restorative therapy" CEC-ZH No. 2011-0150/5.) After 2 years a maximum of 3 fillings should be replaced due to poor quality.
- The rate of loss of vitality after 1 year is maximum 1%, which corresponds to a frequency as described in the literature.

The clinical investigation will be conducted with a maximum of 75 patients. No more than two restorations will be placed in any one patient. For inclusion and exclusion criteria, see item "7.3 Participants".

Recalls take place after 6, 12, 24, 60 months.

Aftercare

At the end of the study period or when patients leave the study, they will continue to be routinely cared for by their private dentist.

3. Justification for the structure of the clinical investigation

In summary, it can be concluded from the literature cited in the investigator's brochure that restorative composites are suitable for the intended indications and show a clinically acceptable performance.

Up to now, polymerization of the adhesive or a composite increment takes 5 to 40 seconds, depending on the material used and the polymerization lamp used to cure the material. Currently, the upper limit of available light intensities for direct restorations is approximately 2'000 mW/cm². In a recent study from Norway (Kopperud et. al, 2017), in which 740 dentists from the public sector were interviewed, it was shown that these dentists exposed each composite increment for an average of 27 s.

In the experimental fillingsystem F-Composite 2, the components are cured with the new Bluephase PowerCure polymerization light. In the special flash mode, the Bluephase PowerCure emits blue light with an intensity that is 1.7 times higher than that of the Bluephase Style 20i, the most powerful light unit from Ivoclar Vivadent AG to date. The Bluephase PowerCure polymerization light emits 3000 mW/cm² and thus allows the materials to be cured in 3 seconds in combination with F-Composite 2, a flowable composite and Adhese Universal.

As the laboratory tests and technical data of the F-Composite 2 system have shown promising results (recorded in investigator's brochure), clinical results are now to be collected. The main focus is on the frequency of occurrence of postoperative hypersensitivities, the investigation of edge quality and surface behaviour.

The fillings are examined and evaluated after certain times (recalls) according to defined criteria. The clinical performance and the clinical success of the restorative material are measured.

4. Investigators

The principal investigator is [name]. [name] and the other investigation-site team members will place resp. evaluate the restorations. An investigator-blinding is carried out during the evaluation of the fillings during recall: the examiner does not know who placed the fillings. All follow-up examinations and the baseline findings are performed by an experienced evaluator. (stated in 7.1 (b))

5. Materials

a) F-Composite 2 and the flowable composite are light-curing composite materials for direct restorative therapy in dentistry. Adhese Universal is a universal adhesive which ensures the adhesion of composites to enamel and dentin. It is indicated for direct and indirect restorative therapy. According to the EC Directive on Medical Devices 93/42/EEC, Annex IX, Rule 8, 1st indent, it is a Class IIa medical device. The flowable composite and Adhese Universal have already been on the market for some time and have proven their worth. What is new here is the polymerization in only three seconds. F-Composite 2, on the other hand, is a newly developed material that does not yet bear the CE mark.

Bluephase PowerCure is a polymerization light which emits blue light in higher intensity than the most powerful light unit Bluephase Style 20i from Ivoclar Vivadent AG (2000 mW/cm² in turbo mode). The Bluephase PowerCure polymerization light emits 3000 mW/cm². It is also a Class IIa medical product, which is not yet CE certified.

F-Composite 2, the flowable composite, Adhese Universal and Bluephase PowerCure are a coordinated system consisting of composite restoratives and adhesive system as well as an LED polymerization unit that allows composite layers up to 4 mm thick to be cured in only 3 seconds for posterior restorations.

Details of the composites and the adhesive

- Composition
- Indication
- Contraindication
- Side effects
- Interactions

as prepared in the provisional Instructions for Use for clinical investigation of F-Composite 2, a flowable composite and Adhese Universal.

Details of the polymerization lamp

- Product overview
- Security
- Commissioning
- Operation
- Maintenance and cleaning
- Product specification

as prepared in the provisional Instructions for Use for clinical investigations of Bluephase PowerCure

b) The four products (F-Composite 2, a flowable composite, Adhese Universal and Bluephase PowerCure) are manufactured by the dental company Ivoclar Vivadent AG, [name].

c) The batch numbers of the materials used and of the lighting unit can be recorded in CRF I.

d) Traceability during and after testing is ensured by batch numbers (filling materials) and serial numbers (equipment).

e) Intended purpose in the planned clinical investigation:

The restorative materials F-Composite 2 and the flowable composite are intended for direct restorative therapy in the posterior region (Class I and II cavities). The Bluephase PowerCure polymerization light is designed for high-energy bulk curing of the F-Composite 2 material, the flowable composite and Adhese Universal when used in Class I and II cavities.

f) populations and indications for which the test product is intended:

Any person between 18 and 65 years of age, who is eligible for the indication "Class I or II posterior filling", can be treated. The gender distribution should be 40-60% women and 40-60% men (see also point 7.3).

g) The test products F-Composite 2 and the flowable composite are composites which consist mainly of inorganic fillers and monomers. In addition, they contain additives, initiators, stabilizers and pigments. Details on the composition can be found in the Instructions for Use for F-Composite 2 and the flowable composite. When used as directed, the material comes into contact with tooth structure, i.e. with dentin and enamel. Dentin and enamel are pretreated with the established bonding agent (Adhese Universal). The products F-Composite 2 and the flowable composite do not contain any human or animal substances or derivatives and also no biologically active substances.

h) General dental training is sufficient for the application of the F-Composite 2 system. Within the framework of this training, the placement of fillings with a composite is state of the art nowadays. The handling of the Bluephase PoweCure polymerization light is trained in the course of monitoring on the basis of the provisional Instructions for Use.

i) there are no specific medical or surgical procedures associated with the use of the test device

6. Risks and benefits of the investigational product and the clinical investigation

a) Participation in this clinical investigation could have the following benefits: The F-Composite 2 system allows a shorter treatment time. On the one hand, the risk of unintentional slippage of the light guide on the filling during the reduced exposure time could be reduced, which would contribute to the safe curing of the composite. On the other hand, it could be easier for the practitioner to keep the surgical field dry during the reduced exposure time of the composite. Both factors could increase the process reliability and thus the quality of composite fillings. These benefits must be weighed against the risks mentioned below.

It is also essential that the treatment and all follow-up examinations are free of charge and that the study recalls ensure regular monitoring of the general dental findings.

b) No foreseeable adverse effect(s) of the product are known.

c) Risks associated with the test product itself are listed in the Instructions for Use F-Composite 2, the flowable composite and Adhese Universal under the heading 'Side effects' and under the heading 'Warning'. All risks also exist when conventional products are used in direct restorative therapy. Due to the high light intensity of the polymerization unit, the gradient of temperature changes in the pulp is increased. It is possible that the patient may feel this if no local anaesthesia is applied. The patient decides whether the procedure is performed under anaesthesia or not. According to in vitro experiments, the maximum temperature reached in the pulp is comparable to conventional polymerization devices. If the energy input is too high, the pulp could suffer thermal damage. Therefore, within 30 s, the Bluephase PowerCure can only be exposed twice in a row for 3 seconds each time. This lock can be manually unlocked by the dentist if the clinical situation requires it. Thermal damage to the soft tissue can be ruled out in Class I and II when used as intended, since the distance between the optical fibre and the tissue is sufficient in these situations. The polymerization of cervical fillings is not indicated.

Last update: 09.10.2020

(adjusted English Version of German Version, LL3027336) Page 6 / 16

No in vitro examination can serve to conclusively assess the risk of postoperative hypersensitivity. Therefore this study must be carried out.

d) There are no risks in connection with participation in the clinical investigation other than those mentioned under a)-c).

e) Possible interactions with concomitant medical treatments are not expected.

f) If the Instructions for Use for F-Composite 2, the flowable composite, Adhese Universal and for Bluephase PowerCure are followed, there are no further measures to be taken to control or mitigate the risks.

g) risk/benefit justification.

The F-Composite 2 system is a novel material or technology with which no clinical experience is yet available. Despite thorough laboratory tests, undesirable effects cannot be excluded. For example, post-operative discomfort or inflammation or the death of the pulp (the "tooth nerve") could occur, or cracks could appear in the tooth structure or between the tooth and the restoration, or marginal gaps could occur which could lead to discoloration, secondary caries, filling fracture, filling loss or tooth fracture.

Unexpected changes in the filling surface could result in roughness, discoloration or increased wear of the material.

Components of the restorative materials used or the adhesive could cause sensitization and allergies (information is contained in the corresponding instructions for use).

The high light energy of the Bluephase PowerCure could cause overheating or burning of the irradiated tissue, resulting in damage to the pulp, the periodontium or the gums.

Flash Composite 2 has been thoroughly tested for possible toxicological and mutagenic properties. Based on the available knowledge, there is no risk to the patient for reasons of toxicology and mutagenicity.

7. Structure of the clinical investigation

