7.5 Specifications for monitoring

This clinical investigation will be monitored by the sponsor at defined timely intervals. The Monitoring Plan lists the activities within the scope of monitoring.

8. Statistical considerations

- a) Due to the study design, no special statistical methods are necessary.
- b) The sample size is 75 fillings
- c) validity of the clinical investigation: the system is suitable for the market if the acceptance criteria are met.
- d) Expected drop-out rate: Analysis of older comparable studies show that an annual drop-out rate of 2% can be expected. Accordingly, three fillings could no longer be checked after 2 years.
- e) Acceptance criterion for post-operative hypersensitivity after 4 weeks: $\leq 10\%$ (=6 fillings).
Acceptance criterion for loss of vitality after 1 year: maximum 1 restored tooth
Acceptance criterion for filling replacement after 2 years: maximum 3 fillings
- g) If more than 50% of the patients suffer from postoperative hypersensitivity after placing at least 20 fillings, the study would be terminated.
- k) If patients discontinue the study or drop out for other reasons (including extraction of the tooth from a cause not related to the study, change of the opposing dentition or treatment by an external dentist), they are considered a drop-out and are reported separately with the drop-out cause (CRF V).
The recall data obtained up to the time of withdrawal from the study are used in the evaluation.

9. Data management

- a) Data verification is carried out with plausibility checks. The data is encrypted, since the patient names do not appear in the data tables, but the cases can be assigned using case numbers and patient IDs.
- c) The archiving of the data takes place on the company's secure servers. The data is stored as SPSS data sheets in anonymized form. The traceability is given by case numbers.
- d) The retention period of the data after completion of the study is 10 years.

Since all persons involved in the study, especially the operators and the evaluator, are familiar with and apply the company's internal guidelines regarding "Good Documentation Practice" (SOP-00081-EN; Good Documentation Practice), the traceability of changes is ensured by the dating and sizing of corrections.

CRFs, radiographs and clinical images will be collected as source data in this study.

Authorities and the Monitor will be granted access to the original data at any time, should this be necessary.

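### The sample-size formula is worked for 5% versus 0% hypersensitivity, not the stated 10% versus 5%, so 75 fillings have roughly 24–39% power rather than 80%

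*Combined protocol and SAP*

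**What the plan says.** Section 1 b) sets the inputs: "Assuming that a maximum of 10% post-operative hypersensitivity is acceptable, but actually only 5% is expected, the following formula can be used". The operating characteristics are given as "80% power, using a chi-square test at 5% probability of error". The formula is then printed as "N = (1.96 * \sqrt{0.95 * 0.05} + 0.84 * \sqrt{1 * 0})^2 / (1 - 0.95)^2 = 73". After an allowance for 2% drop-out in the first year, the section concludes that "75 fillings are necessary at the beginning of the study to statistically confirm the primary endpoint".

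Section 8 b) repeats the figure: "The sample size is 75 fillings". The 10% limit is also the working hypothesis for hypersensitivity at one month (sections 1 c) and 2) and the acceptance criterion at four weeks (section 8 e), where it is equated with 6 fillings). Section 7.1 describes a single-arm study with postoperative hypersensitivity as the primary endpoint, so a one-sample comparison with a fixed rate is the relevant calculation.

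**The concern.** The sentence and the formula describe different hypotheses. In the sentence the proportion free of hypersensitivity is 0.90 under the null and 0.95 under the alternative. In the formula those proportions are 0.95 and 1. The 10% limit, which is the rate the study is meant to rule out, never enters the calculation.

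This is the only power statement for the primary endpoint. A reader, an ethics committee or a regulator would take from it that, if the true rate is 5%, the study has an 80% chance of showing statistically that the rate is below 10%. If the formula does not deliver that, the stated basis for 75 fillings falls away, and a 5%-level test would more often than not fail to exclude 10% even when the product performs as expected.

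**Working it through.** **Inputs.** From section 1 b): null rate 10%, expected rate 5%, power 80% (z = 0.84), error 5% with z = 1.96 as printed, drop-out 2%. The text does not say whether the test is one- or two-sided. The 1.96 implies two-sided 5%; z = 1.645 is shown as the one-sided alternative.

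**Formula.** For a one-sample proportion with null p0 and alternative p1:

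N = (z_α √[p0(1 − p0)] + z_β √[p1(1 − p1)])² / (p0 − p1)²

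**1. The plan's own figure.** With the printed entries:

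- numerator: (1.96 × √0.0475 + 0.84 × 0)² = (1.96 × 0.2179)² = 0.1825
- denominator: 0.05² = 0.0025
- N = 72.99, rounded up to 73; 73 / 0.98 = 74.5, rounded up to 75

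The arithmetic reproduces exactly, so the formula has not been garbled in reading. In event rates it is 5% versus 0%. Since √(1 × 0) = 0, replacing 0.84 with any other power multiplier still gives 72.99.

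**2. The stated rates in the same formula.**

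- z = 1.96: (1.96 × 0.3 + 0.84 × 0.2179)² / 0.0025 = (0.588 + 0.183)² / 0.0025 = 237.8, so **238** (238 / 0.98 = 242.9, so 243 with drop-out)
- z = 1.645: (0.4935 + 0.1831)² / 0.0025 = 183.1, so **184** (184 / 0.98 = 187.8, so 188 with drop-out)

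Other variants for 10% versus 5% (continuity correction, null and alternative swapped, variance taken at one rate only, arcsine, two-arm) do not give 73 either. The smallest is 117.5.

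**3. Normal-approximation power at 75 fillings.**

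Power = Φ((0.05 × √75 − z_α × 0.3) / 0.2179), with 0.05 × √75 = 0.4330

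- z = 1.96: Φ(−0.711) = **0.239**
- z = 1.645: Φ(−0.278) = **0.391**

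**4. Exact binomial at 75 fillings.**

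| Conclude below 10% if events are | Probability at true 10% | Probability at true 5% |
|---|---|---|
| ≤ 2 | 1.6% | 27.0% |
| ≤ 3 | 5.04% | 48.0% |
| ≤ 6 (section 8 e) | 36.7% | 91.9% |

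A test that keeps its error at or below 5% must reject only at 2 or fewer events, which gives 27% power. The exact test first reaches 80% power at 179 fillings (one-sided 5%) or 231 (one-sided 2.5%).

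**5. Precision at 75 fillings.** If 4 of 75 (5.3%) are hypersensitive, the exact 95% confidence interval is 1.5% to 13.1%, which includes 10%.

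**The case against.** The strongest reply is that no significance test decides the study. Section 8 a) says nothing special is needed by way of statistical methods, and section 8 e) accepts on a count. On 75 fillings that count rule passes a product with a true 5% rate 91.9% of the time, so low test power does not mean the study will probably miss its primary criterion. That is right, and the power figures here should not be read that way. But the same rule also passes a true 10% rate 36.7% of the time. It is not a rule with 5% error, and it cannot support section 1 b), which promises statistical confirmation.

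A second reply is that 73 is a legitimate precision calculation. It does equal the number needed for a 95% confidence half-width of 5 points around 5%: 1.96² × 0.0475 / 0.0025 = 72.99. The plan does not say this, however. It names power and a chi-square test, and no section explains entering 5% and 0%.

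Third, the 39% figure is a smooth approximation on a one-sided reading that the plan does not state. An uncorrected one-sided z test would reject at 3 or fewer events and have 48% power. That is a fair qualification, but its true error is 5.04%, just over the limit, and 48% is still far from 80%. The figure tied to the plan's own 1.96 is 24%, or 27% exactly.

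**Conclusion.** The concern holds. The printed calculation is correct arithmetic for hypotheses other than those stated, and the 80% power plays no part in its result. For 10% versus 5% the required number is 238 fillings at the plan's own z-value (184 one-sided), about 3.3 (2.5) times the 73 printed. With 75 fillings the power is 24% (z = 1.96) or 39% (z = 1.645) by normal approximation, and 27% by an exact test.

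These figures assume that all 75 fillings are evaluable and independent. Losses would lower the power slightly: at 73 fillings the approximations are 23% and 38%. Up to two fillings per patient are allowed, so positive correlation within patients would lower it further. The figures concern a formal test against 10%, not the chance of meeting the count criterion in section 8 e).

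**What to change.** In section 1 b):

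- Put 0.90 × 0.10 under the first root, 0.95 × 0.05 under the second, and (0.95 − 0.90)² in the denominator. Print the result, 238.
- Keep 75 fillings, and say plainly that this is fewer than the formula requires and on what other ground it is retained (for example feasibility or precision).
- Delete the 80% power claim and the statement that 75 fillings are needed for statistical confirmation.
- State instead that 75 fillings give about 24% power for 10% versus 5% at two-sided 5% (27% by exact test), and that 4 events in 75 would give an exact 95% confidence interval of about 1.5% to 13%.

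It would help to add beside the criterion in section 8 e) that up to 6 of 75 is met with probability 91.9% at a true 5% and 36.7% at a true 10%, so that the count rule is not mistaken for a 5%-level test.

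The cost is a change of protocol wording, with no added patients or procedures, and a much less favourable stated power. Section 10 counts changes to the statistical design among those needing prior Ethics Committee approval, so the correction probably has to go through that route.

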7.1 General information

a) It is a single-arm clinical investigation without a control or comparison group. This design was chosen because clinical studies ("Clinical investigation of Flash Composite in direct restorative therapy" CEC-ZH No. 2011-0150/5; "Clinical investigation of AdheSE One F Upgrade in direct restorative therapy" CEC-ZH_NR. 2012-0076) with direct fillings have already been conducted by the same dentists in the same institution. Accordingly, existing data regarding the quality of fillings can be used for comparison purposes. The chosen study design allows higher case numbers, which seems reasonable in view of the primary endpoint.

b) An investigator-blinding is carried out during the evaluation of the fillings during recall: the examiner does not know who placed the fillings. All follow-up examinations and the baseline findings are performed by an experienced evaluator.

c) Primary endpoint: postoperative hypersensitivity

Secondary end points: devitalization and therefore necessary endodontic treatment, quality of filling and therefore necessary replacement of fillings

d) The following assessment criteria shall apply:

Baseline Findings

The participants are recalled 7-10 days after placing the filling to record the baseline findings. In addition to the clinical examination, the participants are also questioned regarding sensitivity

to temperature and occlusion. The aesthetic integration of the filling is evaluated, the occlusion is checked and corrected if necessary. Photos of the restoration are also taken. For the baseline findings and for all recalls, the restorations are examined and evaluated (SQUACE and FDI criteria) using a special evaluation sheet.

On the findings sheet, the patient has to draw the sensitivity of the tooth in everyday life regarding temperature and bite sensitivity on an unscaled straight line of 10 cm. The distance from the left edge (zero point = no discomfort or pain) is measured to within 1 mm in the evaluation.

In the semi-quantitative evaluation of the fillings (SQUACE=SemiQUantitative Clinical Evaluation), the following findings are documented: secondary caries FDI 12, marginal gap FDI 6.b, marginal deficits FDI 6.c, marginal discoloration FDI 2.b and marginal fracture FDI 6.a (in each case as a percentage of the total margin)

The following FDI criteria are assessed using the FDI rating system

- Postoperative hypersensitivity or tooth vitality FDI 11
- Surface gloss FDI 1

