- Surface discoloration FDI 2a
- Colour match and translucency FDI 3
- Fracture of material and filling retention FDI 5
- Proximal contact point FDI 8
- Patient satisfaction FDI 10
- Tooth integrity (tooth cracks and fractures) FDI 13

Based on the FDI System for Clinical Evaluation of Restorations (Hickel et al 2007, 2010), evaluations are assigned for each FDI criterion according to the following scheme

1= clinically ideal

2= clinically good

3= clinically acceptable

4= no longer clinically acceptable (but repairable)

5= clinically unacceptable, restoration must be replaced (repair not possible or not practical)

Horizontal cracks are plotted on the printout of oral or vestibular photographs of the tooth (before and after the filling is placed or during recall) and compared with the preoperative findings.

Follow-up examinations

Recalls take place after 6, 12, 24, 60 months. The restorations are evaluated according to the above criteria.

Photos are taken of all restorations at the examination appointments. If a patient suffers from postoperative complaints, the patient is examined again 14-20 or 30-35 days after the filling has been placed.

e) No special test equipment is used for the assessment of the test variables.

f) instructions for the exchange of participants are not required and no exchange takes place

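### The claim of filling quality comparable to F-Composite is decided only by an absolute limit of 3 replacements, with no F-Composite rate, margin or comparison, so a pass does not establish it

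*Combined protocol and SAP*

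**What the plan says.** Section 1(c), repeated in section 2, lists among the performance to be demonstrated that the system "enables a filling quality at least comparable to F-Composite", and names an earlier study of that material. The next sentence reads "After 2 years a maximum of 3 fillings should be replaced due to poor quality".

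Section 7.1 a) describes the design: "It is a single-arm clinical investigation without a control or comparison group". It justifies this by earlier studies from the same dentists and institution, and says that "existing data regarding the quality of fillings can be used for comparison purposes".

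Section 8 turns the quality hypothesis into one line, in item e): "Acceptance criterion for filling replacement after 2 years: maximum 3 fillings". Item a) says "Due to the study design, no special statistical methods are necessary", and item c) says "the system is suitable for the market if the acceptance criteria are met".

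Section 7.1 d) provides for SQUACE findings (percentages of the filling margin) and FDI scores from 1 to 5 at baseline and at every recall. Score 4 is defined as "4= no longer clinically acceptable (but repairable"); score 5 means that the filling has to be replaced. No acceptance criterion uses the FDI scores or the SQUACE findings to judge filling quality.

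**The concern.** The hypothesis is comparative and the rule is absolute. To conclude that one material is at least as good as another, one needs the other material's result, a margin and a way to set the two side by side. Section 7.1 a) points to existing data, but section 8 never takes them up. What the documents report of the F-Composite study is its curing condition, its three-year observation and the absence of permanent pulp damage. They give no replacement rate, score distribution or number of fillings.

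The rule is also narrower than filling quality. A filling may reach a state that the plan's own scale calls unacceptable, be repaired, and leave the count of replacements unchanged.

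Section 8 c) makes market suitability depend on the acceptance criteria. Followed as written, the plan would attach a comparative conclusion to a count that cannot support it.

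**Working it through.** **The plan's own figures.** The limit of 3 comes with no derivation, so there is nothing to reproduce for it. The only calculated figure is the sample size in section 1(b): (1.96 × √(0.95 × 0.05) + 0.84 × 0)² / 0.05² = 3.8416 × 0.0475 / 0.0025 = 72.99, rounded up to 73, and 73 / 0.98 = 74.5, rounded up to 75. It reproduces, but it concerns postoperative hypersensitivity and says nothing about filling quality.

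**Inputs.**
- 75 fillings: section 8 b).
- 2% drop-out per year, three fillings no longer checked at 2 years: section 8 d). This leaves n = 75 − 3 = 72.
- Limit c = 3: section 8 e).
- F-Composite replacement rate: not given. Rates of 1%, 2% and 4% are assumed below.
- Share of unacceptable fillings that are repaired rather than replaced: not given. A range from none to two thirds is assumed below.
- Fillings are treated as independent, although section 7.3 allows two per patient.

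**Step 1: what the limit allows.** 3/72 = 4.2%, exact (Clopper-Pearson) 95% CI 0.9% to 11.7%. With all 75 fillings it is 4.0% (0.8% to 11.2%).

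**Step 2: the chance of passing.** P(pass) = P(X ≤ 3), with X binomial (72, p).

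| True 2-year replacement rate p | P(pass) |
|---|---|
| 1% | 99% |
| 2% | 94% |
| 3% | 83% |
| 4% | 67% |
| 5% | 51% |
| 8% | 16% |
| 10% | 6% |

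**Step 3: against assumed F-Composite rates.**

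| Assumed F-Composite rate | Pass if equal | Pass if double |
|---|---|---|
| 1% | 99% | 94% |
| 2% | 94% | 67% |
| 4% | 67% | 16% |

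At an assumed 1%, a system with triple the rate (3%) passes 83% of the time. At an assumed 4%, an equal system fails 100 − 67 = 33% of the time. Whether the rule is lenient or strict depends entirely on a figure that the documents do not give.

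**Step 4: fillings scored 4.** Let f be the true proportion of fillings that become unacceptable (score 4 or 5) by 2 years, and s the share of them repaired rather than replaced. The replacement rate is then p = f × (1 − s). With f = 10% (assumed):

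| Share repaired s | p | P(pass) |
|---|---|---|
| none | 10.0% | 6% |
| one third | 6.7% | 28% |
| half | 5.0% | 51% |
| two thirds | 3.3% | 78% |

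For illustration, 3 fillings replaced and 10 scored 4 and repaired give 13/72 = 18% unacceptable, and the criterion is still met.

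**Step 5: the cause of replacement.** Sections 1(c) and 2 restrict the count to replacements for poor quality; section 8 e) names no cause. Three quality replacements and one for another reason would pass under sections 1(c) and 2 and fail under section 8 e).

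**The case against.** The limit of 3 may itself be the sponsor's working definition of comparable, drawn from the earlier study or from the investigator's brochure, neither of which is among the documents. Section 8 e) labels it a criterion for replacement, not for comparability. This has weight: the documents do not show that 3 is the wrong number. But without a reference figure nobody can check the link, and the decision rule belongs in section 8 wherever its source lies.

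On score 4, a reader might infer that such fillings are repaired by rule and never count, so that any number of them passes. The text does not go that far. It says repairable, contains no repair rule, and does not tie replacement to score 5. A filling scored 4 could be replaced and would then count. What stands is that the limit need not count them. The size of the effect depends on the repaired share, which is why a range is shown and no single share is taken as the estimate.

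A reader might also infer that the existing data would settle comparability if only they were analysed. The documents do not support that. They do not show that the earlier study recorded the same FDI criteria or had a 24-month assessment. Section 1(d) says it cured the filling material at 10 000 mW/cm² for one second without exposing the adhesive, whereas here adhesive and composites are cured at 3000 mW/cm² for 3 s each. An unadjusted difference between the two studies would not be like for like.

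On the cause of replacement, section 7.1 c) links replacement to filling quality, and sections 7.3 c) and 8 k) treat extraction for unrelated reasons and treatment by an external dentist as drop-out. The mismatch is real but narrow.

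**Conclusion.** The concern holds in this form: the plan makes a comparative claim about filling quality, and its only rule for that claim is an absolute count with no F-Composite rate, margin or comparison. A count of 3 in 72 is compatible with true replacement rates from 0.9% to 11.7%. Under assumed F-Composite rates, the same rule passes a system with three times a 1% rate 83% of the time and fails a system equal to a 4% rate 33% of the time.

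In addition, the limit may miss unacceptable fillings that are repaired. At 10% true failure the chance of passing runs from 6% to 78% as the repaired share goes from none to two thirds. These figures rest on n = 72, independent fillings, and assumed values for the F-Composite rate, the failure rate and the repaired share. Two fillings in one patient may be correlated, which would change the figures somewhat.

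The documents do not show that the system is worse than F-Composite, that the limit of 3 is badly chosen as an absolute criterion, or that many fillings would be repaired. The point concerns a secondary endpoint. It should still be corrected, because market suitability depends on it.

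**What to change.** 1. Keep the limit of 3 as an absolute performance criterion, and add to section 8 e) the restriction to poor quality already used in sections 1(c) and 2.
2. Delete the comparability claim from sections 1(c) and 2, unless an F-Composite reference rate and a margin are fixed beforehand and written into section 8.
3. Add to section 8 the proportion of fillings replaced or scored 4 or 5 on the filling-quality criteria by 24 months, with an exact 95% CI. List those criteria by FDI number. Leave out FDI 11, because hypersensitivity and vitality have their own endpoints. Report the SQUACE marginal findings alongside, since they are recorded as percentages of the margin and a composite of the criteria scored 1 to 5 would miss them.
4. Where matching F-Composite data exist, report the difference with a 95% CI as descriptive, and state that the earlier study used different curing.

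The cost is protocol wording and a little more analysis of data already collected, with no new patients, visits or measurements. The downside for the sponsor is a narrower claim and a reported failure rate that may look less favourable.
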